## **STATISTICAL CONSIDERATIONS FOR RWE-003 STUDY**

The study hypothesis was that treatments of migraine with the Nerivio device In adolescents will demonstrate similar results to the results previously found in adults

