**Study RWE-003**

Title	Real-World Evidence (RWE) of Usage of Nerivio, a Remote Electrical Neurostimulation (REN) Device In Adolescents Patients With Migraine
Sponsor	Theranica Bio-Electronics Ltd. [name]
Investigational Device	
Nerivio is a Remote Electrical Neuromodulation (REN) wearable, battery-powered medical device for the acute and/or preventive treatment of migraine with or without aura in patients 12 years of age or older. Nerivio is controlled by a mobile application. Nerivio is intended for self-administration in a home healthcare environment.
 
The device is worn on the upper arm and transmits transcutaneous remote electrical nerve stimulation by applying weak electrical pulses that invoke conditioned pain modulation (CPM) to inhibit migraine pain. Nerivio is intended for self-administration at the onset of a migraine episode.

Objectives	To evaluate the safety, utilization and efficacy of Nerivio in adolescent patients (Age 12-18) who used the Nerivio device for treating their migraine
Patient Population	Nerivio users aged 12-18 years old who registered a Nerivio account and used the Nerivio device for the acute treatment of migraine.
Sample size	The sample size will includes all Nerivio users in the age of 12-18 in the Nerivio database who treated with Nerivio at least once between Jan 01, 2021 and May 31, 2022
Inclusion criteria	

• Age between 12-18 years

• REN user across the United States who created Nerivio account on January 1st, 2021 until May 31, 2022.

• Had at least two evaluable treatments with the Nerivio device (for consistent efficacy analysis).

Exclusion criteria	

• Treatments shorter than 20 minutes will not be included in the analysis

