Study Design	
The analysis included patients at the age of 12-18 (at the day of opening a Nerivio account) with migraine across the USA who used Nerivio at least once between January 01, 2021, and May 31, 2022.
 
Treatment data will be collected through the Nerivio app (Nerivio®) which is required for treatment. Device output current is set by the user to be strong but not painful and is equivalent to treatment dosage (max device current 40 mA on 0-100 units user-facing scale). Additionally, patients can voluntarily log details about their symptoms at both treatment onset and 2-hours post-treatment status. Treatment efficacy will be measured by consistent reduction in headache pain intensity and functional disability at 2-hours post-treatment, based on data from patients who voluntarily will answer the pre and post treatment questionnaires. Safety will be assessed by the rate of device related adverse event reported by the patients.

Evaluable Treatment	
Evaluable treatment is a treatment that meets all the following criteria:
 

• Baseline and 2-hour post-treatment pain intensity and functional disability scores were recorded.

• The participant did not use any concomitant acute migraine medication during the treatment.

Efficacy endpoints	

1. Pain Relief: Reduction in pain intensity from moderate or severe (baseline score of 2 or 3) to mild or no pain (score of 1 or 0) at 2 hours post-treatment.

2. Pain Freedom: Reduction in pain intensity from mild, moderate, or severe (baseline score of 1, 2, or 3) to no pain (score of 0) at 2 hours post-treatment.

3. Functional Disability Relief: Reduction in functional disability by at least one point from baseline at 2 hours post-treatment.

4. Functional Disability Freedom: Reduction in functional disability from mild, moderate, or severe (baseline score of 1, 2, or 3) to no disability (score of 0) at 2 hours post-treatment.

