Utilization endpoints	

5. Consistent Usage of Migraine Abortive (Rescue) Medications: The proportion of subjects with REN treatments without the use of pharmacological migraine abortive (rescue) medication (either over the counter or prescribed), or with a combination of rescue medication or without any treatment at all at 2 hours post-treatment in at least 50% of all their treatments.

6. Treatment intensity distribution: The mean intensity of the stimulation collected for all treatments that were performed within the study

Safety endpoints	Rate of serious adverse events, adverse events and device-related adverse events

Data collection	
Data will be collected prospectively through the Nerivio smartphone application. At the time of creating a Nerivio account on the App, patients (and their parents, in case of patients younger than 18) are required to sign a consent statement presented to them, where they agree that their deidentified data may be collected and used for reserve purposes.
 
Prospective data was collected for Nerivio users in the United States who treated their migraine attacks with the Nerivio device. Nerivio utilization, and Nerivio treatment reports at T=0h and T=2h were extracted from the Nerivio server in an unidentified manner. Data will be analyzed per user following additional analysis per the target population.
 
The following data will be extracted:
 

• Demographics: Age at registration, gender.

• Treatment Details: Treatment date, baseline pain intensity, pain intensity at 2 hours post-treatment, baseline functional disability, functional disability at 2 hours post-treatment.

• Treatment Frequency: Number of treatments per month over the 12-months period.

• Pain Intensity: 0 (no pain), 1 (mild), 2 (moderate), 3 (severe).

• Functional Disability: 0 (no disability), 1 (mild interference), 2 (moderate interference), 3 (severe interference).

• Additional migraine symptoms (Nausea/ vomiting, Photophobia, Phonophobia)

Statistical considerations	See at the end of the document
Responder Definition	For each efficacy endpoint, a participants will be considered a responder if they achieved the defined outcome in at least 50% of their evaluable treatments during that study period.

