## STATISTICAL ANALYSIS

### **Demographic and Baseline Analysis**

Demographic and baseline condition related characteristics will be tabulated and compared between the participant data types. Continuous variables will be summarized by a mean, standard deviation, minimum, median and maximum and categorical variables by a count and percentage.

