### **Efficacy Endpoints Analysis**

Generalized linear mixed model (GLMM) will be used to compare the effect of treatment month on efficacy rate outcomes.

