### **Utilization Endpoints Analysis**

Utilization outcome will be calculated from the treatment parameters (intensity levels) and the treatment reports (usage of rescue medications), and will be presented in appropriate distribution tables.

Qualifies treatment was defined as

1 - Attacks treated with Nerivio for at least 20 minutes

2 - Pre and post treatment data were reported by the participant for the specific treatment

3 – No rescue medications were taken before and during the 2 hours post treatment, according to the participant report

Consistent efficacy will be conducted in cases where at least two qualified treatments were performed. Patients who experienced the outcome (e.g., pain freedom) in at least 50% of their reported treatments, during which they did not report the use of rescue medications, were considered responders.

Headache pain and functional disability will be rated at baseline and at 2 h post-treatment on a 4-point scale: severe, moderate, mild, or none. Migraine associated symptoms (photophobia, phonophobia, and nausea/vomiting) will be marked as present or not.

Pain relief will be calculated as a decrease from severe or moderate levels at baseline to mild or none at 2 h posttreatment.

Functional disability relief will be calculated as any improvement in disability from baseline to 2 h posttreatment.

Pain/functional disability freedom will be calculated as a decrease from any pain/disability level at baseline to none at 2 h post-treatment.

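### The only stated hypothesis is similarity to adults, but no endpoint is designated for that comparison and no adult rate, margin or adult analysis is planned

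*Combined protocol and SAP*

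**What the plan says.** The hypothesis, at the start of Statistical Considerations for RWE-003 Study, is that "treatments of migraine with the Nerivio device In adolescents will demonstrate similar results to the results previously found in adults". It does not say whether efficacy, utilization or safety results are meant, which adult results, or how close counts as similar.

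The rest of the plan concerns adolescents only:

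- **Objectives** (synopsis): "To evaluate the safety, utilization and efficacy of Nerivio in adolescent patients (Age 12-18) who used the Nerivio device for treating their migraine". Adults are not mentioned.
- **Sample size** (synopsis): "all Nerivio users in the age of 12-18 in the Nerivio database" with at least one treatment in the study window. No number, power or precision basis is given.
- **Efficacy, Utilization and Safety endpoints** (synopsis): four efficacy endpoints (pain relief, pain freedom, functional disability relief, functional disability freedom), plus utilization and safety endpoints. None is tied to the hypothesis.
- **Responder Definition** (synopsis): a participant responds "if they achieved the defined outcome in at least 50% of their evaluable treatments during that study period". Utilization Endpoints Analysis adds: "Consistent efficacy will be conducted in cases where at least two qualified treatments were performed".
- **Efficacy Endpoints Analysis**: "Generalized linear mixed model (GLMM) will be used to compare the effect of treatment month on efficacy rate outcomes". This is the whole section.
- **Demographic and Baseline Analysis**: "Demographic and baseline condition related characteristics will be tabulated and compared between the participant data types". The data types are not defined.

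**The concern.** A hypothesis of similarity needs four things before the results are known: the outcome to compare, the reference value and its uncertainty, the largest difference that still counts as similar, and the rule for deciding. The plan supplies candidate outcomes without choosing among them, and supplies none of the other three.

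If the report says that adolescents responded like adults, the endpoint, adult figure and tolerance will all have been chosen outside the plan. One observed rate could then be called similar or not similar, depending on those choices. The statement would not be a test of the hypothesis, although it stands as the hypothesis in the statistical section.

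**Working it through.** **1. Does any section fill the gap?** The plan states no figure to reproduce, so the first check is of the text.

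| Section | What it provides | Does it compare with adults? |
|---|---|---|
| Sample size; Patient Population | Users aged 12-18 | No adult data enter |
| Efficacy endpoints | Four outcomes per treatment | None designated |
| Responder Definition | 50% of a participant's own treatments | No: a within-person threshold, not an adult rate or margin |
| Efficacy Endpoints Analysis | Mixed model for treatment month | No: a contrast over time within adolescents |
| Demographic and Baseline Analysis | Baseline characteristics by data type | No: not outcomes |
| Safety Endpoints Analysis | Device-related events divided by participants | No reference value |
| Utilization Endpoints Analysis | Distribution tables and definitions | No reference value |

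The synopsis sends the reader to the end of the document for statistics, and these sections are that end.

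**2. How much do the missing choices matter?** All inputs here are assumptions: 270 of 500 adolescents respond (54%), and the adult rate is 60%, treated as known. The Wilson interval is

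[p + z²/2n ± z√(p(1−p)/n + z²/4n²)] / (1 + z²/n).

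With p = 0.54, n = 500 and z = 1.645 (90%):

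- centre = (0.54 + 0.00271)/1.00541 = 0.5398
- half-width = 1.645 × √(0.0004968 + 0.0000027)/1.00541 = 0.0366
- interval for the rate = 50.3% to 57.6%
- minus 60 = **-9.7 to -2.4 points**

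Conclude similar only if this interval lies inside ± the margin:

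| Margin (points) | Verdict |
|---|---|
| 5 | not similar |
| 10 | similar, by 0.3 points |
| 15 | similar |

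The 10-point verdict is fragile. With a 95% interval the same data give 49.6% to 58.3%, or -10.4 to -1.7 points, which fails at 10. The contrast between 5 and 15 points holds at either confidence level.

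**3. Adult uncertainty.** With a Newcombe interval and the same rates, the 90% interval is -10.09 to -1.94 if the 60% comes from 2,000 adults and -11.1 to -0.9 if it comes from 500. Both fail at 10 points, the first by 0.09. This shift is specific to the inputs. With 1,000 adolescents the lower bounds are -8.6 (known), -9.2 (2,000 adults) and -10.4 (500 adults). With 200 adolescents the bound is already -11.8 with the adult rate known, so all three fail.

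**4. Sample size.** For equivalence to a fixed rate with no true difference, one-sided 5% tests and 80% power, n = p(1−p)(1.645 + 1.282)²/m². At p = 0.5 this gives 857, 215 and 96 for margins of 5, 10 and 15 points. At p = 0.3 or 0.7 it gives 720, 180 and 80. Whether the available users are enough therefore depends on a margin that the plan does not give.

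**5. Could a non-significant difference stand in for similarity?** No. With assumed true rates of 60% and 50%, a two-sided 5% test is non-significant with probability 0.71 at 100 per group and 0.48 at 200 per group.

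**The case against.** The best reply is that this is a descriptive real-world study. Its objective does not mention adults, no endpoint or analysis depends on the hypothesis sentence, and nothing shows that a similarity claim will be published. On that reading the sentence is a loosely worded expectation. Much of this stands: the responder rates serve the objective as they are, and the harm arises only if similarity is reported. It does not remove the mismatch, because the sentence is presented as the study hypothesis in the statistical section and the planned analyses cannot address it.

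Three stronger readings are not supported:

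- **That the plan has no outcomes.** It defines efficacy, utilization and safety endpoints and a responder rule. What is missing is the designation of any of them for the adult comparison.
- **That the adolescent rates had already been seen.** A reader might infer this from past-tense wording such as "The analysis included patients at the age of 12-18 (at the day of opening a Nerivio account". But tenses are mixed throughout, collection and analysis are also described in the future, and the past tense is used for plain definitions. At most, some extraction may have taken place. Nothing shows that rates had been calculated.
- **That the adult denominator generally decides the verdict.** In the illustration it does so only for some inputs, and one case turns on a bound of -10.09. Dependence on the margin is the firmer point.

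Equivalence is also not the only legitimate form. A one-sided non-inferiority reading of *similar* is defensible, and the plan does not say which is meant.

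**Conclusion.** The point holds and should be fixed. The stated hypothesis and the planned analyses do not match: the plan, followed exactly, yields adolescent rates and a treatment-month contrast, and neither can show similarity to adults. That conclusion rests on the text alone and needs no assumed number.

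Its size cannot be computed from the documents. In the illustration the verdict on identical data reverses between a 5-point and a 15-point margin. That rests on the assumed 54%, 500 adolescents and known adult rate of 60%, and it shows only that the missing choices can decide the answer. The descriptive results are not undermined.

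**What to change.** **Default.** Replace the hypothesis with a descriptive aim, for example: *The study will describe responder rates in users aged 12-18; no conclusion of similarity to adults will be drawn.* Add to Efficacy Endpoints Analysis that each responder rate is reported with a 95% confidence interval. For an assumed 54%, the Wilson interval would be 44.3% to 63.4% with 100 participants and 49.6% to 58.3% with 500. The cost is a change of wording, intervals on rates already planned, and giving up any similarity claim.

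**Only if the claim is to be kept:**

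1. Reconcile the medication criterion first. Evaluable Treatment in the synopsis excludes acute medication taken while the treatment is under way. The definition of a qualified treatment under Utilization Endpoints Analysis excludes rescue medication both beforehand and throughout the following 2 hours. An adult rate cannot be matched until one rule for a countable treatment applies.
2. Name the endpoint or endpoints, say whether utilization or safety is included, and say whether all must meet the criterion.
3. Fix an adult responder rate and its denominator under that same rule, including the 50% threshold and the minimum of two qualified treatments.
4. Set a justified margin and a confidence-interval decision rule (equivalence or non-inferiority) that includes adult uncertainty.
5. Label the comparison post hoc if adolescent rates are already known.

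This route may need an adult data extraction, since the documents give no adult figure, and the claim may fail even when it is true. With assumed rates of 60% in both groups, a 10-point margin and the 90% interval rule, similarity is concluded with these probabilities:

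| Adolescents | Adult rate known | 500 adults |
|---|---|---|
| 100 | 32% | 20% |
| 200 | 81% | 58% |
| 300 | 94% | 76% |
| 500 | over 99% | 89% |

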## **DATA COLLECTION**

## **BASELINE DATA**

Baseline participant characteristics (age, gender) will be collected from the Nerivio account of each participant.

## UTILIZATION DATA

Utilization information is pulled out from the Nerivio server for each treatment

## TREATMENT DATA

Treatment data will be retrieved from the Nerivio app for each treatment. Data includes automatic parameters (e.g time of treatment, location, device serial number, treatment intensity etc...) and individual information completed by the participant (pain level before and after the treatments, migraine symptoms, functional disability before and after the treatment etc...)

## SAFETY DATA

All safety information will be pulled out from the Nerivio support center and/or additional safety reports from other sources that are registered in Nerivio database.

## STATISTICAL ANALYSIS

### **Demographic and Baseline Analysis**

Demographic and baseline condition related characteristics will be tabulated and compared between the participant data types. Continuous variables will be summarized by a mean, standard deviation, minimum, median and maximum and categorical variables by a count and percentage.

### **Safety Endpoints Analysis**

The rate of device related adverse event (DRAE) will be calculated as the number of reported DRAE divided by the number of participants in the study.

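### The only planned safety rate counts device-related adverse events per participant with no exposure term, so it mixes device risk with how long and how often users treated

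*Combined protocol and SAP*

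**What the plan says.** Safety is the first-named objective in the synopsis. The Safety endpoints row lists "Rate of serious adverse events, adverse events and device-related adverse events" without a denominator. The Study Design row is equally general: "Safety will be assessed by the rate of device related adverse event reported by the patients". The one formula is in the Safety Endpoints Analysis, where the DRAE rate is "calculated as the number of reported DRAE divided by the number of participants in the study". The numerator is a count of events; the denominator is a count of people.

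The synopsis sets who those people may be. The Sample size row takes users "who treated with Nerivio at least once between Jan 01, 2021 and May 31, 2022". The inclusion criteria take each "REN user across the United States who created Nerivio account on January 1st, 2021 until May 31, 2022", and also ask for two or more evaluable treatments, tied to the consistent-efficacy analysis. The Exclusion criteria row removes treatments of less than 20 minutes from the analysis, without saying which analysis. The Data collection row mentions a 12-month period, but for treatment frequency.

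Session data are available: "Utilization information is pulled out from the Nerivio server for each treatment". The Treatment Data section adds that parameters such as time and intensity of treatment are captured automatically. Adverse events come from the support center and other registered reports (Safety Data section).

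**The concern.** Events caused by a stimulation device can arise only when it is used. If risk accrues with use, a person with one session in the last week of the window and a person with many months of sessions have very different chances of an event, yet each adds one to the denominator. Two cohorts with the same risk per treatment could then show different rates because one registered later or treated less often. Because the numerator counts events, it can keep growing with use while the denominator stays fixed.

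At stake is whether the main safety figure can be interpreted. A low value could mean a safe device or little use of it, and the plan does not ask for the exposure figures that would let a reader tell which. This is separate from under-reporting and from repeat events in one user: it would remain with complete reporting and at most one event each.

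**Working it through.** The plan states no sample size, expected DRAE rate or treatment frequency, so it has no figure of its own to reproduce. The check asks how far the planned rate moves when device risk is held fixed.

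**Inputs from the documents**
- Window: 1 January 2021 to 31 May 2022 inclusive = 516 days; 516 / 30.4375 = 16.95 months, taken as 17.
- Minimum exposure: one treatment (Sample size row) or two evaluable treatments (inclusion criteria).
- Possible cap: 12 months (Data collection row, for treatment frequency).

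**Assumptions, not in the documents**
- Data cut on 31 May 2022, so a user's follow-up is 17 months minus the time of registration.
- Constant risk r = 0.001 DRAE per treatment (0.0005 to 0.002 also tried) and k = 2 treatments per month.
- Registration time as a fraction of the window: early Beta(1,2), uniform, or late Beta(2,1). These are moderate patterns.

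**Formula.** Events per 100 participants = 100 × r × k × mean months of follow-up.

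**Mean follow-up.** The mean registration fraction is 1/3, 1/2 and 2/3, so mean follow-up is 17 × 2/3 = 11.3, 17 × 1/2 = 8.5 and 17 × 1/3 = 5.7 months. With a 12-month cap the means are 10.0, 7.8 and 5.5.

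| Registration | Mean months | DRAE per 100 participants | With 12-month cap | DRAE per 1,000 treatments |
|---|---|---|---|---|
| Early | 11.3 | 2.27 | 2.00 | 1.0 |
| Uniform | 8.5 | 1.70 | 1.55 | 1.0 |
| Late | 5.7 | 1.13 | 1.10 | 1.0 |

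Early against late: 2.27 / 1.13 = 2.0-fold, or 2.00 / 1.10 = 1.8-fold with the cap. These ratios do not depend on r or k. The per-treatment rate is the same in every row.

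**Does the planned rate still respond to device risk?** Yes. With uniform registration and k = 2, r = 0.0005, 0.001 and 0.002 give 0.85, 1.70 and 3.40 per 100. It is proportional to risk as well as to exposure.

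**If users stop treating.** With exponential discontinuation (assumed mean use of 3 or 6 months, no cap), mean active time is 2.82 (early) against 2.13 (late) months, or 4.84 against 3.17. The ratio falls to 1.3 or 1.5.

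**If events cluster at first use.** Let a share s of events occur at first use and set the uniform-registration rate to 1.00 per 100. The rate is then s + (1 − s) × (mean months / 8.5).
- s = 0.5: early 0.5 + 0.5 × 11.33 / 8.5 = 1.17; late 0.5 + 0.5 × 5.67 / 8.5 = 0.83; ratio 1.4.
- s = 1: 1.00 under every pattern.

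**The case against.** Events per participant is a legitimate descriptive summary, and this is a single cohort with no comparison arm. The spread above compares hypothetical cohorts; it is not a bias of that size in the figure the study will report. That stands, and it is why the per-participant rate should be kept.

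A per-treatment rate also has a weakness. Sessions are logged automatically while events reach the database through the support center and similar reports, so a passively collected numerator would sit over a near-complete denominator. Heavy users who tolerate the device would carry most of the weight. That stands too, and argues for a supplementary rate rather than a replacement.

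Three stronger readings are tempting and are not supported:
- A reader might infer that the rate tracks registration dates instead of device risk. It tracks both: doubling the risk doubles the rate.
- A reader might infer a threefold distortion. That needs strongly skewed registration (Beta(1,3) against Beta(3,1): 12.75 / 4.25 months = 3.0), no discontinuation and even accrual of events with use. Discontinuation with mean use of 3 or 6 months brings even those patterns to 1.6- or 1.9-fold.
- A reader might infer that the rate cannot be set against the adult results named in the study hypothesis. The hypothesis does not mention safety, and the documents give neither the adult follow-up nor the adult denominator. If the adult rate was also per participant, the planned figure would be the matching metric.

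Nor is it settled that one-session users are in the denominator: the two-evaluable-treatments criterion may remove them. That leaves wide variation in exposure and adds an undefined safety population to the problem.

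**Conclusion.** The concern holds in a limited form. The planned DRAE rate has no exposure term, no common safety follow-up is stated, and no per-treatment or person-time rate is planned alongside it. The figure can be calculated as written, but it mixes device risk with length and frequency of use.

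Under moderate registration patterns, constant risk per treatment, continued use and a cut on 31 May 2022, the mixing is worth about 2.0-fold, or 1.8-fold with a 12-month cap. It falls to 1.3- to 1.5-fold with the assumed discontinuation (no cap), to 1.4-fold if half of events occur at first use, and to nothing if all do. The documents do not say which applies. Reporting both rates with the exposure would make the result readable in any of these cases. This is a cheap improvement to the plan and does not invalidate the planned rate.

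**What to change.** In the Safety Endpoints Analysis:

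- Keep the per-participant DRAE rate.
- Add beside it DRAEs per 1,000 treatments, with a 95% interval that allows for clustering within participants (participant-level bootstrap or Poisson model with robust errors), or an exact Poisson upper limit if there are no events.
- Report median sessions and median months of follow-up per user.
- Name the safety population: all users with at least one treatment, or only those with two evaluable treatments.
- State the data cut-off for sessions and for safety reports.

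In the synopsis, state that the exclusion of treatments under 20 minutes applies to efficacy, so that logged short sessions count as safety exposure. Without this the two sections conflict, and a session cut short by an event could drop out of the denominator. The sponsor should confirm that the server retains such sessions, since the documents do not say so explicitly.

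The cost is some plan wording and a few table rows from data already extracted. The downside is that two rates need explaining, and the per-treatment rate must carry a note that events are passively reported while sessions are logged automatically.

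### The device-related adverse event rate is events per participant, not the share of users affected, and no safety population or AE/SAE calculation is defined

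*Combined protocol and SAP*

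**What the plan says.** The Safety endpoints row of the synopsis names three measures: "Rate of serious adverse events, adverse events and device-related adverse events". The Study Design row narrows this to one: "Safety will be assessed by the rate of device related adverse event reported by the patients". Safety Endpoints Analysis gives the only calculation, the DRAE rate as "the number of reported DRAE divided by the number of participants in the study". It states no interval, no rule for repeat reports, and no definition of who counts as a participant in the study.

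The cohort is described in two ways. The Sample size row takes "all Nerivio users in the age of 12-18 in the Nerivio database who treated with Nerivio at least once" in the study window, and Study Design likewise speaks of at least one use. The Inclusion criteria row adds a criterion that opens "Had at least two evaluable treatments with the Nerivio device (for consistent efficacy analysis"; its parenthesis ties it to efficacy. For a treatment to be evaluable, "Baseline and 2-hour post-treatment pain intensity and functional disability scores were recorded" must hold, and no acute migraine medication may have been used alongside it. The Exclusion criteria row adds "Treatments shorter than 20 minutes will not be included in the analysis", with no exception for safety.

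Under Safety Data, adverse event reports come from the support center and from other registered reports, not from the treatment questionnaires.

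**The concern.** The formula has events on top and people below. A reader of the results will take such a rate as the chance that an adolescent user has a device-related event, and it is not that quantity. Users treat repeatedly, so one user can contribute more than one report, and no planned count of affected users would show it.

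The denominator matters for a related reason. Someone who tries the device, has an unpleasant event and stops may have one session, a session under 20 minutes, or no 2-hour scores. These are the users a safety analysis most needs to keep, and the plan does not say whether they are in.

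Finally, two of the three named safety rates have no stated method, although this short section is the whole safety analysis in a population aged 12 to 18.

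**Working it through.** **Figures in the plan.** The documents give no number of users, no event count and no expected safety rate, so there is no figure to reproduce. All counts below are assumptions chosen to show the mechanism.

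**Step 1: numerator.** Let N be the number of users, a the number with at least one DRAE, and m the mean number of events per affected user.

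- Planned rate = a × m / N
- Share of users affected = a / N
- Ratio = m

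With N = 1,000 and a = 10, the share affected is 10/1,000 = 1.0% (Clopper-Pearson 95% CI 0.48% to 1.83%).

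| Events per affected user (m) | Planned rate | Share affected |
|---|---|---|
| 1 | 1.0% | 1.0% |
| 1.5 | 1.5% | 1.0% |
| 2 | 2.0% | 1.0% |
| 3 | 3.0% | 1.0% |

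The same point with the reports fixed: 10 reports among 1,000 users give 1.0% under the formula whether they come from 10 users (share 1.0%, CI 0.48% to 1.83%) or from 2 users with five each (share 0.2%, CI 0.02% to 0.72%).

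**Step 2: denominator.** Compare the two candidate cohorts.

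- All treated users: Sample size and Study Design, at least one treatment.
- Restricted users: the listed inclusion criterion, at least two evaluable treatments.

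The parenthesis in that criterion, and Utilization Endpoints Analysis, which applies the two-treatment rule to consistent efficacy, favour the first for safety. Neither is named as the safety population, and the 20-minute exclusion refers to the analysis in general.

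To see what a restricted set would do, let f be the fraction of users who qualify and s the fraction of affected users who qualify, with one event each:

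- Restricted rate = (a × s) / (N × f), which is the true share multiplied by s/f

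It is too high if s exceeds f and too low if s is below f. With N = 1,000, a = 10 and f = 0.4 (assumed), the denominator is 400:

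| s | Restricted rate (true share 1.0%) |
|---|---|
| 0 (all affected users left out) | 0/400 = 0% |
| 0.5 | 5/400 = 1.25% |
| 1 (all retained) | 10/400 = 2.5% |

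Keeping every report over the restricted denominator also gives 10/400 = 2.5%. Across f = 0.2 to 0.8 the rate runs from 0% to 5.0% (10/200). The documents fix neither f nor s, so they settle neither direction nor size.

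**Step 3: endpoints against analyses.**

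| Endpoint named | Calculation given |
|---|---|
| SAE rate | none |
| AE rate | none |
| DRAE rate | events over participants |

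**The case against.** Events per participant is a legitimate descriptive quantity, and the sponsor may have meant participants with a DRAE. If events are rare and each affected user reports once, the two figures coincide. The plan does not say that repeat reports are counted separately; it has no rule for them. All of that is fair. It limits the likely size of the problem, but the written formula still does not give the share affected, and no other planned table does.

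Several stronger readings are tempting and should be resisted.

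- A reader might infer that users who stop after one session are excluded from the safety denominator. The documents do not say so. The two-treatment criterion carries an efficacy qualifier, and Sample size, Study Design and Utilization Endpoints Analysis point to an all-user cohort. What stands is that the safety population is undefined.
- A reader might infer that the rate is inflated, for example by 1/0.6 = 1.7 to 1/0.4 = 2.5 times if 40% to 60% of users qualify. That needs the less favoured denominator, an assumed qualifying share, and reports kept from all users over a smaller base. Safety Data describes where reports come from, not which users are counted. If early stoppers' events are dropped with them, the rate falls instead.
- A reader might infer an invalid confidence interval. The plan specifies none for safety.
- A reader might rank safety above the other aims because the objective names it first. That is list order; no ranking is stated.

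**Conclusion.** The concern holds in this form. The stated DRAE formula is mean events per participant, and it overstates the share of users affected by a factor equal to the mean number of events per affected user. This follows from the wording, provided each report counts as an event. The actual factor is unknown and is 1 if every affected user reports once.

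The denominator is an ambiguity, not a stated exclusion. If a restricted set were used, bias could go either way; the 0% to 5.0% range around a true 1.0% is an illustration on assumed counts, not an estimate.

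The lack of any calculation for the AE and SAE endpoints needs no assumption. It is mainly missing detail, but it should be filled in. None of this shows that the reported safety result will be wrong by a material amount; it shows that the plan does not make that result interpretable as a risk per user.

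**What to change.** In Safety Endpoints Analysis:

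1. Define the DRAE rate as the number of users aged 12-18 with at least one DRAE, divided by all such users with at least one started session in the study window, whatever the session length or questionnaire status. Take numerator and denominator from the same cohort, and give an exact (Clopper-Pearson) 95% CI.
2. State that the two-evaluable-treatment criterion and the 20-minute exclusion do not apply to safety.
3. Report event counts separately, for example DRAEs per 1,000 started sessions, labelled as an event rate.
4. Apply the same measures to the AE and SAE endpoints.

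This costs some wording and a few table rows, with no change to study conduct. The real cost is linkage. Safety reports come from the support center and other sources, while the Data collection row describes app data extracted without identification. The documents do not show that a report can be tied to an account, an age or a session, so this should be checked first. Reports that cannot be linked should be listed separately and left out of the per-user rate.
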